6.2 Toxicity Management

The toxicity management of the AEs including AEs of special interest consists of safety monitoring (review of AEs on an ongoing basis, and periodical/ad hoc review of safety issues by a safety data monitoring committee), and if applicable, interruption of study drug dosing with appropriate clinical management and/or discontinuation of the subjects from study drug. The management of specific AEs and laboratory parameters is described below.

For subjects who discontinue study drug but continue study participation and are on standard of care therapies, these toxicity management requirements do not apply (including alerts from the central lab) and any intolerability to standard of care therapies should be managed by the prescribing physician.

Serious Infections: Subjects should be closely monitored for the development of signs and symptoms of infection during and after treatment with study drug. Study drug should be interrupted if a subject develops a serious infection. A subject who develops a new infection during treatment with study drug should undergo prompt diagnostic testing appropriate for an immunocompromised subject. As appropriate, antimicrobial therapy should be initiated, and the subject should be closely monitored. Study drug may be restarted once the infection has been successfully treated. Subjects who develop active TB must be permanently discontinued from study drug.

Herpes Zoster: If a subject develops herpes zoster, consider temporarily interrupting study drug until the episode resolves.

Gastrointestinal Perforation: Subjects presenting with the onset of signs or symptoms of a gastrointestinal perforation should be evaluated promptly for early diagnosis and treatment. If the diagnosis of gastrointestinal perforation (other than due to appendicitis or mechanical injury) is confirmed, the subject must be permanently discontinued from study drug.

Major Cardiovascular Event: For subjects who develop a major cardiovascular event (MACE: acute myocardial infarction, cerebrovascular accident [stroke]) while on study drug, the investigator should

evaluate the benefit/risk of, and discuss with the TA MD whether it is appropriate to continue study drug.

Malignancy: Subjects who develop malignancy other than NMSC or carcinoma in situ of the cervix must be permanently discontinued from study drug. Information including histopathological results should be queried for the confirmation of the diagnosis. Periodic skin examination is recommended for subjects who are at an increased risk for skin cancer. Subjects who develop malignancies should be referred to appropriate specialists and managed as per standard of care.

Muscle-related symptoms: If a subject experiences symptoms suggestive of myositis or rhabdomyolysis, consider checking CPK and aldolase with clinical management and/or study drug interruption as deemed appropriate by the investigator.

Thrombosis Events: Subjects who develop symptoms of thrombosis should be promptly evaluated and treated appropriately. If the diagnosis of deep vein thrombosis, pulmonary embolus or noncardiac, non-neurologic arterial thrombosis is confirmed, the subject must be discontinued from study drug.

ECG Abnormality: Subjects must be discontinued from study drug for an ECG change considered clinically significant and with reasonable possibility of relationship to study drug, OR a confirmed absolute QT interval corrected for heart rate using Fridericia's formula (QTcF) value > 500 msec.

COVID-19: Study drug should be interrupted in subjects with a confirmed diagnosis of COVID-19. Consider interrupting study drug in subjects who show signs and/or symptoms with suspicion of COVID-19. Study drug may be restarted once the infection has resolved, or 5 days have passed since the COVID-19 positive test result (whichever comes last). The COVID-19 eCRF must be completed.

Management of Select Laboratory Abnormalities: For any given laboratory abnormality, the Investigator should assess the subject, apply the standard of care for medical evaluation and treatment following any local guidelines. Specific toxicity management guidelines for abnormal laboratory values are described in Table 3, and may require a supplemental eCRF to be completed. For subjects with ongoing laboratory abnormalities which require data entry into an eCRF, an additional eCRF related to subsequent laboratory abnormalities is only required if the subject has relevant changes in history (e.g., new onset signs or symptoms) or laboratory values which have returned to normal reference range or its Baseline value followed by subsequent laboratory abnormalities meeting toxicity guidelines (considered a new event). All abnormal laboratory tests that are considered clinically significant by the investigator will be followed to a satisfactory resolution. If a repeat test is required per Table 3, the repeat testing must occur as soon as possible.

Table 3. Specific Toxicity Management Guidelines for Abnormal Laboratory Values

Laboratory Parameter	Toxicity Management Guideline for Upadacitinib and Matching Placebo
Hemoglobin	 If hemoglobin < 8 g/dL, interrupt study drug dosing and confirm by repeat testing with a new sample. If confirmed, continue to withhold study drug until hemoglobin value returns to ≥ 8 g/dL. OR
	 If hemoglobin decreases ≥ 3.0 g/dL from baseline without an alternative etiology, interrupt study drug dosing and confirm by repeat testing with new sample.
	 If hemoglobin decreases ≥ 3.0 g/dL from baseline and an alternative etiology is known or the hemoglobin value remains in the normal reference range, the subject may remain on study drug at the investigator's discretion.
	 If confirmed, continue to withhold study drug until hemoglobin value returns to within 3.0 g/dL from baseline.
Absolute neutrophil count (ANC)	 If confirmed < 1000/μL by repeat testing with new sample, interrupt study drug dosing until ANC value returns to ≥ 1000/μL.
	 For confirmed < 500/µL, if value returns to ≥ 1000/µL, restarting study drug is allowed if there is an alternative etiology identified; documentation should include reason rechallenge is expected to be safe for the subject. Study drug should be discontinued if no alternative etiology can be found.
Absolute lymphocyte counts (ALC)	If confirmed < 500/ μ L by repeat testing with new sample, interrupt study drug dosing until ALC returns to \geq 500/ μ L.
Total white blood cell count	If confirmed < 2000/ μ L by repeat testing with new sample, interrupt study drug dosing until white blood cell count returns to $\geq 2000/\mu$ L.
Platelet count	If confirmed < 50,000/μL by repeat testing with new sample, interrupt study drug dosing until platelet count returns to normal reference range or its baseline value.

Laboratory Parameter	Toxicity Management Guideline for Upadacitinib and Matching Placebo
Aspartate aminotransferase	Interrupt study drug if any of the following scenarios are confirmed by repeat testing of AST/ALT:
(AST) or alanine aminotransferase	ALT or AST > 3 × ULN and either a total bilirubin > 2 × ULN or an international normalized ratio (INR) > 1.5:
(ALT)	 A separate blood sample for INR testing will be needed to measure INR at the time of repeat testing for ALT or AST. A repeat test of INR is not needed for determination if above toxicity management criteria are met.
	 If a creatine phosphokinase (CPK) value is not available, a CPK should be drawn to exclude AST/ALT elevations related to muscle injury
	 ALT or AST > 3 × ULN along with new appearance of fatigue, nausea, vomiting, right upper quadrant pain or tenderness, fever, rash, and/or new-onset eosinophilia.
	ALT or AST > 5 × ULN for more than 2 weeks.
	If ALT or AST > 8 × ULN, interrupt study drug immediately, repeat testing with a new sample, and if repeat test confirms result contact the TA MD.
	Subjects with HBc Ab+ (irrespective of HBs Ab status) and negative HBV DNA at screening who develop the following should have HBV DNA by PCR testing performed within 1 week (based on initial elevated value):
	• ALT > 5 × ULN OR
	 ALT or AST > 3 × ULN if an alternative cause is not readily identified.
	 A separate blood sample for HBV DNA PCR testing will be needed at the time of repeat testing for ALT or AST.
	A positive result for HBV DNA PCR testing will require immediate interruption of study drug (unless not acceptable by local practices). Within 1 week of the first episode of a positive HBV DNA PCR test, a hepatologist consultation should occur for recommendation regarding subsequent treatment.
	Subjects who meet any of the above criteria should be evaluated for an alternative etiology of the ALT or AST elevation and managed as medically appropriate. The investigator should contact the AbbVie TA MD to discuss the management of a subject when an alternative etiology has been determined. The alternative etiology should be documented appropriately in the eCRF. If ALT or AST values return to the normal reference range or its Baseline value, study drug may be restarted. If restarting study drug, documentation should include reason rechallenge is expected to be safe. Study drug should be discontinued if no alternative etiology can be found and ALT or AST elevations persist.
	For any confirmed ALT or AST elevations > 3 ULN, complete the appropriate supplemental hepatic eCRF(s).
Serum Creatinine	• If serum creatinine is > 1.5 × the baseline value and > ULN, repeat the test for serum creatinine (with subject in an euvolemic state) to confirm the results. If the results of the repeat testing still meet this criterion, then interrupt study drug and re-start study drug once serum creatinine returns to ≤ 1.5 × baseline value.
	For the above serum creatinine elevation scenarios, complete the appropriate supplemental renal eCRF(s).

Laboratory Parameter	Toxicity Management Guideline for Upadacitinib and Matching Placebo
Creatine Phosphokinase	Investigators should complete the supplemental elevated CPK eCRF for the below CPK elevation scenarios or if CPK increase is considered to be an AE by the investigator.
	 If a subject experiences any symptoms suggestive of myositis or rhabdomyolysis, blood for measuring CPK and aldolase levels should be drawn with clinical management as deemed appropriate by the investigator.
	 If confirmed CPK value ≥ 4 × ULN and there are no symptoms suggestive of myositis or rhabdomyolysis, the subject may continue study drug at the investigator's discretion after evaluation.
	 If CPK ≥ 4 × ULN accompanied by symptoms suggestive of myositis or rhabdomyolysis, interrupt study drug and contact AbbVie medical monitor.

Urgent and Emergency Surgeries

For urgent and emergency surgeries the following rules will apply:

- If the subject must undergo an urgent or emergency surgery, the study drug should be interrupted at least 1 week prior to a planned urgent surgery if possible, or at the time of an emergency surgery. After surgery, allow reintroduction of study drug once the physician has examined the surgical site and determined that it has healed and there is no sign of infection.
- Elective surgery, and interruption of study drug for such a surgery, should be avoided until after
 the Week 52 visit has been completed. If elective surgery is considered prior to the primary
 endpoint visit, it must be discussed with the TA MD and performed with TA MD approval. If the
 subject undergoes elective surgery, the study drug should be interrupted at least 1 week prior to
 the planned surgery. Allow reintroduction of study drug once the physician has examined the
 surgical site and determined that it has healed and there is no sign of infection.

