5.4 Prior and Concomitant Therapy

Any medication or vaccine (including over the counter or prescription medicines, vitamins and/or herbal supplements) that the subject is receiving within 30 days prior to Screening and/or receives during the study must be recorded along with the reason for use, date(s) of administration including start and end dates, and dosage information including dose, route and frequency must be recorded in the eCRF. Also, medications taken for GCA since date of diagnosis (based on subject recollection and available medical records) should be entered into the appropriate eCRF inclusive of the dates of first and last dose, maximum dosage taken, route of administration and reason for discontinuation, if known.

Subjects must be consented for the study prior to discontinuing any prohibited medications for the purpose of meeting study eligibility.

Throughout the study, addition of a biologic or non-biologic immunomodulators other than CS while taking blinded study drug (upadacitinib or PBO) is not permitted for rescue.

Inhaled and nasal CS for stable medical conditions are allowed during the study but must have been at a stable dose for \geq 4 weeks prior to the Baseline Visit. Short-term use (\leq 10 days) of CS (oral, inhaled, nasal, intravenous, or intramuscular) for non-GCA-related conditions for events such as exacerbation of asthma or chronic obstructive pulmonary disease, allergic reactions, or serious infection when additional CS may be required to prevent adrenal insufficiency (a total of up to 100 mg of prednisone or equivalent

through 52 weeks in Period 1 and a total of up to 100 mg of prednisone or equivalent through 52 weeks in Period 2) is allowed during the study.

Subjects should be treated with anti-platelet therapy (aspirin or clopidogrel) at the discretion of the investigator and in accordance with local standard-of-care practice.

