5.8 Study Drug

Study drug includes the investigational product (IP) of upadacitinib and matching upadacitinib PBO as well as CS therapy (open label or blinded prednisone/prednisolone and matching CS PBO) included as part of the protocol-defined CS taper.

Study drug will be taken orally once daily beginning on Day 1 (Baseline) and should be taken at approximately the same time each day, with or without food. Subjects will be instructed to return all drug containers (even if empty) to the study site personnel at each study visit; study site personnel will document compliance.

AbbVie will supply upadacitinib, matching upadacitinib PBO, as well as open-label and blinded CS therapy (prednisone or prednisolone) and matching CS PBO included as part of the protocol-defined CS taper.

All study drug (IP and CS) must be stored at controlled room temperature (15° to 25°C/59° to 77°F). US sourced prednisone 20 mg will need to be stored protected from light and moisture. Study drug will be packaged in quantities sufficient to accommodate study design.

In cases of state of emergency or pandemic situations, study drug shipment can be made from the study site to the subject if allowed by local regulations. Refer to the Operations Manual in Appendix G for details on direct-to-patient (DTP) shipment of study drug.

Each kit will be labeled per local requirements and this label must remain affixed to the kit. Upon receipt, study drug should be stored as specified on the label and kept in a secure location. Each kit will contain a unique kit number. This kit number is assigned to a subject via interactive response technology (IRT) and encodes the appropriate study drug to be dispensed at the subject's corresponding study visit. All blank spaces on the label will be completed by the site staff prior to dispensing to subjects. Study drug will only be used for the conduct of this study.

Upon completion of or discontinuation from study treatment, all original study drug units (containing unused study drugs) will be returned to the sponsor (or designee) or destroyed on site. All return or destruction procedures will be according to instructions from the sponsor and according to local regulations following completion of drug accountability procedures.

Individual study drug information is presented in Table 2.

Table 2. Identity of Study Drug

	Investigational Product (IP)	IP	IP Placebo (PBO)	Corticosteroid (CS)	cs	CS PBO

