In addition to the AESIs listed above, the following adverse events will also be monitored during the study: Bone Fracture; Retinal detachment.

Adverse Event Severity and Relationship to Study Drug

Investigators will rate the severity of each AE according to the National Cancer Institute Common Terminology Criteria for Adverse Events (CTCAE) version 5.0, which can be accessed at: http://ctep.cancer.gov/protocolDevelopment/electronic applications/ctc.htm#ctc.

If no grading criteria are provided for the reported event, then the event should be graded follows:

Mild (Grade 1) Asymptomatic or mild symptoms; clinical or diagnostic observations only;

intervention not indicated

Moderate (Grade 2) Minimal, local or noninvasive intervention indicated; limiting age-

appropriate instrumental activities of daily living (ADL)

Severe (Grade 3 – 5)

Grade 3 Severe or medically significant but not immediately life-threatening;

hospitalization or prolongation of hospitalization indicated; disabling; limiting self-care ADL (self-care ADL refer to bathing, dressing and undressing, feeding self, using the toilet, taking medications, and not

bedridden)

Grade 4 Life-threatening consequences; urgent intervention indicated

Grade 5 Death related to AE

The investigator will assess the relationship of the AE to the study drugs upadacitinib (or matching placebo) and prednisone/prednisolone (or matching placebo). Summary of CS-related AEs will be based on this assessment.

The investigator will use the following definitions to assess the relationship of the AE to the use of study drug:

Reasonable Possibility – After consideration of factors including timing of the event, biologic plausibility, clinical judgment, and potential alternative causes, there is sufficient evidence (information) to suggest a causal relationship.

No Reasonable Possibility – After consideration of factors including timing of the event, biologic plausibility, clinical judgment, and potential alternative causes, there is insufficient evidence (information) to suggest a causal relationship.

For causality assessments, events assessed as having a reasonable possibility of being related to the study drug will be considered "associated." Events assessed as having no reasonable possibility of being related to study drug will be considered "not associated." In addition, when the investigator has not reported a causality or deemed it not assessable, AbbVie will consider the event associated.

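### Protocol 6.2 interrupts study drug for serious infection, COVID-19 and surgery without limiting this to upadacitinib/placebo, so read literally it also pauses the prednisone taper

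*Protocol*

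**What the plan says.** Protocol 5.8 gives the definition: "Study drug includes the investigational product (IP) of upadacitinib and matching upadacitinib PBO as well as CS therapy", the CS being that of the protocol-defined taper, open-label or blinded. Section 6.1 likewise treats prednisone/prednisolone as one of the study drugs when causality is assessed.

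Section 6.2 uses the term without a qualifier:
- Serious infection: "Study drug should be interrupted if a subject develops a serious infection", and "Study drug may be restarted once the infection has been successfully treated".
- COVID-19: "Study drug should be interrupted in subjects with a confirmed diagnosis of COVID-19". Restart waits for resolution or for 5 days after the positive test, whichever is later.
- Surgery: "the study drug should be interrupted at least 1 week prior to a planned urgent surgery if possible". In an emergency, dosing stops when the operation takes place. Elective surgery also has a one-week rule. Restart waits until the site has healed without infection.
- Herpes zoster, suspected COVID-19 and muscle symptoms: the investigator is only asked to consider interruption.

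Table 3, in the same section, is limited by its column heading: "Toxicity Management Guideline for Upadacitinib and Matching Placebo".

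Section 5.4 allows short courses of CS for non-GCA conditions (at most 10 days, and 100 mg in total in Period 1). Its examples include "serious infection when additional CS may be required to prevent adrenal insufficiency".

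**The concern.** A defined term that includes prednisone appears in rules that tell sites to stop dosing during acute illness or around an operation. Every subject enters on at least 20 mg/day of prednisone or prednisolone. A site that applies the 5.8 definition as written would withhold the taper dose when 5.4 foresees that more steroid, not less, may be needed.

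The end of the pause depends on recovery, so its length has no upper limit. Section 5.5 covers CS on permanent discontinuation: sponsor CS stops with upadacitinib/placebo, and the investigator prescribes its replacement. There is no parallel text for a temporary interruption. A site looking for a precedent finds one in which the two components stop together.

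What is at stake is subject safety and the clarity of an instruction that may have to be followed under time pressure.

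**Working it through.** The plan gives no figure on this point, so there is none to reproduce. The check has two parts.

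**Texts side by side**
1. The definition in 5.8 covers both components.
2. The 6.2 rules for serious infection, confirmed COVID-19 and surgery use the defined term, are worded as 'should', and name no component.
3. Table 3 names upadacitinib and placebo only. Section 5.8 adds a parenthesis (upadacitinib or PBO) where it means that component alone. So the protocol does narrow the term in some places, and it does not do so in these rules.
4. Sections 5.4, 5.5, 5.8 and 6.2 and the SAP do not say that the taper continues, or is replaced, during a temporary interruption.

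The literal result is therefore a pause of the taper. It can matter only in Period 1 and only while the scheduled dose is above zero. Open-label escape CS lies outside the definition.

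**Dose that the literal reading would pause**

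The inputs are the daily doses in Appendix E by starting dose. Dose withheld = daily dose × days paused. The 5-day row is an illustrative COVID-19 pause and the 7-day row an illustrative one-week pause, both at the Week 1 dose. Weeks are counted from the Week 1 row, after Baseline.

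| Starting dose (mg) | 20 | 30 | 40 | 50 | 60 |
|---|---|---|---|---|---|
| Week 1 dose, 26-week taper (mg/day) | 15 | 25 | 35 | 40 | 50 |
| Week 1 dose, 52-week taper (mg/day) | 17 | 25 | 35 | 40 | 50 |
| Withheld in 5 days, 26-week / 52-week (mg) | 75 / 85 | 125 / 125 | 175 / 175 | 200 / 200 | 250 / 250 |
| Withheld in 7 days, 26-week / 52-week (mg) | 105 / 119 | 175 / 175 | 245 / 245 | 280 / 280 | 350 / 350 |
| Weeks with dose above 0, 26-week taper | 19 | 21 | 23 | 24 | 25 |
| Weeks with dose above 0, 52-week taper | 45 | 47 | 49 | 50 | 51 |
| Ratio of weeks, 52-week to 26-week | 2.4 | 2.2 | 2.1 | 2.1 | 2.0 |

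Examples: 5 × 15 = 75 mg; 7 × 50 = 350 mg; 45/19 = 2.4; 51/25 = 2.0.

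The daily dose at issue falls with time. It is 4-8 mg (26-week) or 9-10 mg (52-week) at Week 12, 0-1 or 6-7 mg at Week 24, and 0 or 3-4 mg at Week 36. Rows around Weeks 43 to 47 are broken in the text copy and were read from the neighbouring rows. This bears only on the 45 and 47 for the two lowest starting doses on the 52-week taper.

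**Endpoint rules**
- SAP 9.3.1 defines non-adherence to the taper by escape therapy started by the investigator in Period 1, or by more than 100 mg of additional systemic CS for GCA. A paused taper is on neither list.
- CS given for an infection or an operation is CS for a non-GCA indication. Above 100 mg it is intercurrent event 3 in SAP 8.0. For the primary endpoint, data after it are multiply imputed, not set to non-response (SAP Table 1).

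**The case against.** The strongest reply is that context already settles the meaning. Table 3 uses the bare term under a heading restricted to upadacitinib/placebo. Sections 5.5 and 5.8 name CS separately where CS is to stop. Section 5.4 speaks of additional CS in serious infection, which presumes that the background dose continues. The Appendix F entry for Operations Manual 6.4 describes interruption of upadacitinib/matching placebo dosing. The manual itself was not available and may state the rule outright.

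This shows that the intent is probably narrow, and a reader should not infer that the protocol means to withdraw steroids in sick patients. It does not remove the conflict. The 6.2 text carries the broad term, and the 5.5 precedent makes the broad reading plausible.

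Three stronger inferences are tempting, and the documents do not support them:
- *The wording turns subjects into non-responders.* SAP 9.3.1 does count any escape therapy in Period 1. But the non-responder sentence in protocol 5.8 concerns escape for GCA disease, and steroid for infection or surgery falls under 5.4 and intercurrent event 3. Non-response would follow only if a site put the steroid in the wrong category.
- *Because dosing below 20 mg is blinded, a site could not replace a paused dose.* The site knows the starting dose and the week, so only two Appendix E values are possible, at most 7 mg/day apart. Investigators also have direct access to emergency unblinding (5.9).
- *The 100 mg allowance in 5.4 is too small to replace the taper.* It is for CS on top of the taper, so measuring it against the paused dose assumes the reading in dispute.

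The scope is also narrower than a count of the rules suggests. Three of them only say 'consider'. Eligibility criterion 15 excludes planned surgery that would affect study assessments. Section 6.2 defers elective surgery until after the Week 52 visit, when the taper dose is 0 mg.

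**Conclusion.** The wording conflict is real and worth correcting as a patient-safety matter. It rests on three facts in the text: the 5.8 definition includes the taper, the 6.2 rules for serious infection, confirmed COVID-19 and surgery do not limit it, and no available text says that the taper continues. Serious infection and COVID-19 are the main cases.

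At Week 1 a literal reading would pause 15-50 mg/day. The wording can affect a subject for 19-25 weeks on the 26-week taper and 45-51 weeks on the 52-week taper, so the placebo arm is exposed to it about twice as long. The documents do not give the number of interruptions, or how sites have read the rule, so no count of affected subjects can be derived. No effect on the primary endpoint is established. The conclusion would weaken to a consistency edit if the Operations Manual already says that CS continues.

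**What to change.** In the 6.2 rules for serious infection, confirmed COVID-19, and urgent, emergency and elective surgery, replace 'study drug' with 'upadacitinib or matching placebo'. For consistency, do the same in the rules that only ask the investigator to consider interruption (herpes zoster, suspected COVID-19, muscle symptoms).

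Add one sentence: the sponsor-dispensed CS taper, open-label or blinded, continues during the interruption unless the investigator judges otherwise; see 5.4 for additional CS. Check that Operations Manual 6.4 says the same.

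The cost is a wording amendment or a site letter. It needs no new visits, kits or unblinding, because subjects keep taking the CS already dispensed. The SAP stays as it is: 9.3.1 already excludes the IRT-dispensed taper from additional CS. SAP 9.1 reports 428 subjects enrolled, against a target of 420, so the benefit falls to those still on the taper. Their number is not given.
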